12.5 Applicable level of significance

The statistical hypothesis will be verified at a 5% significance level, indicating the corresponding two-sided 95% level confidence intervals (or one-sided 97.5% confidence intervals).

12.6 Procedures with missing/incorrect data

In this study, absent/missing data will not be completed.

12.7 Procedures for reporting any deviations from the original

Statistical Analysis Plan

If there is a deviation from the planned statistical analysis, all changes should be identified in comparison with the methods described in the protocol. Similarly, if there is a need for any additional changes after the analysis, it will be reflected in the study report.

12.8 Selection of patients for analysis

Planned study population/Safety population

All patients taken the study product will be included in the statistical safety analysis, according to the principle of population of the planned treatment.

Per-Protocol Study Population

The research results for each patient will be evaluated for compliance with the protocol, with a discussion of any deviations from the protocol in cases where this has occurred. Criteria for inclusion in the per-protocol population are as follows:

- inclusion in the study in compliance with all the inclusion / non-inclusion criteria;
- conducting the study in strict accordance with the protocol.

13 DIRECT ACCESS TO PRIMARY DATA/DOCUMENTS

The sponsor or a person appointed by the sponsor may conduct an audit / inspection of a clinical trial at clinical centers. Regulators can also conduct an inspection at any time during or after the study. An audit / inspection may include checking documentation at a clinical center, including a CRF and primary documentation.

It is the responsibility of the Investigator to provide direct access to the primary data / documentation for the purposes of monitoring, auditing, examination, and inspection by authorized bodies.

The Investigator's file shall contain the complete information on the study, indicating all events and the time at which they occurred.

13.1 Study completion

The clinical center must complete the study and provide all the required documentation, in full compliance with the protocol and current legislation. The study may be suspended until its completion for objective reasons, both by the Sponsor and the study site. Notifications of suspension of the study should be sent to all parties involved in the study as soon as possible. Any extension of the study period must be agreed between the Sponsor and the study site and documented.

13.2 Protocol Compliance

Investigator shall conduct research in accordance with the protocol developed by the Sponsor and approved by the relevant regulatory authorities. If an amendment to the protocol is planned, the Sponsor must submit all changes in the protocol to the regulatory authorities in accordance with the established requirements.

13.3 Deviations from protocol

In general, any deviation from the protocol can be accepted only in an emergency or after receiving a written agreement from the Sponsor and subject to approval by the Ethics Committee. Any deviation from the protocol should be clearly explained in the primary documentation and in the CRF.

All protocol deviations are classified as “Significant” and “Minor”. Significant deviations from the protocol lead to the unsuitability of the data obtained for analysis. A patient with a significant deviation from the protocol should be excluded from the final analysis.

A slight deviation from the protocol may reduce the quality of the data for analysis, but this data can still be used.

Significant deviations from the protocol include, but are limited to:

- Administration of the medicinal products not provided by the protocol
- Significant deviations from visit schedules, including skipping any visit;
- *Deviation from the visit procedures*

- identification of missed use of the prescribed drug (more than 2 skips for patients taking the drug 2 times a day for the entire period of treatment and more than 4 skips for patients taking the drug 3 times a day for the entire period of treatment);
- inclusion in the study of a patient who does not meet the inclusion and non-inclusion criteria of the protocol.
- conducting the study procedures before obtaining the written informed consent of the patient and his/her parent / adoptive parent;
- other significant deviations according to the Investigator or the Sponsor.

If during the study a situation of a direct threat to the patient's life occurred and the additional prescription of any other drugs other than authorized drugs was required, the monitor of the study and the sponsor of the study should be informed within 24 hours about deviations from the protocol.

In this case, the patient who additionally received drugs that are not authorized by the protocol should be excluded from the final analysis.

The investigator will monitor him/her until the state that caused the protocol violation is resolved.

Minor protocol deviations

All other deviations that are not significant, do not affect the patient's safety and do not substantially violate the procedures provided for by the protocol. Classification of protocol deviations for minor deviations and significant deviations will be made by authorized representatives of the Sponsor after the data on deviations from the Protocol are provided (according to monitoring reports and other sources). A complete list of deviations from the protocol will be approved prior to the start of the statistical analysis and the distribution of patients among the populations for analysis. Deviations from the Protocol are always considered individually with an analysis of the reasons that should be reflected in the primary documentation. The decision to exclude a patient with deviations and violations of the Protocol from the study should be made individually in consultation with the Sponsor of the study.

The decision to include these patients in the statistical analysis is made before closing the database of the study.

If significant deviations from the protocol are found, the patient should be excluded from the final data analysis.

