
Study population and the number of enrolled patients:
	
Patients with a clinically confirmed diagnosis of ARVI (ICD-10 code: J00, J02, J04, J06) will be randomized and assigned to one of two groups at the ratio 1:1: Group 1 - patients will receive the study product as part of complex therapy; Group 2 - patients will receive placebo as part of complex therapy.
 
Calculation of the sample size is based on the following Formula:
 $n = (Z_{\alpha} + Z_{\beta})^2 \cdot \frac{2 \cdot SD^2}{(\mu_o - \mu_p - \delta)^2}$ 
where, Z_{α} and Z_{β} are critical values of the normal distribution corresponding to the established error levels α and β (α- and β-errors are 0.05 and 0.2, respectively), SD - a standard deviation [25 - 28].
 
As a result of calculation based on the above values ($Z_{\alpha}=1.645$, $Z_{\beta}=0.842$, $SD=0.2$ day, $\delta=-0.52$ day, $\mu_o=2.6$ days, and $\mu_p=3.2$ days), the sampling size was obtained that ensures a statistical study power of at least 80%, equal to 78 patients in each group (156 subjects in total). Taking into account the possible dropout of 10% of patients, the sample size will be extended to 86 subjects in each group (172 subjects in total). Calculations were performed using the R v Statistics package. 3.4.3.
 
Taking into account the possible dropout of patients at screening, it is planned to screen 210 patients in the study, of whom 172 will be randomized.

Study sites
	
Medical Technologies Limited Liability Company. Address: [name].
 
State Budgetary Institution of Public Health of Yaroslavl region "Regional Children's Clinical Hospital". Address: [name].
 
Municipal Children's Clinic No. 4. Address: [name].
 
Kurator, Limited Liability Company. Address: [name].
 
St. Petersburg State Budgetary Institution of Public Health "Children's Municipal Hospital No. 22". Address: [name].
 
State Budgetary Institution of Public Health of Yaroslavl region "Municipal Children's Clinical Hospital No. 5". Address: [name].
 
ArsVite Northwest Limited Liability Company. Address: [name].

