9.1.5 Visit 4 (Study completion, Day 12 ± 1)

Visit 4 (Study completion, Day 12 ± 1) shall be held by telephone contact at a time convenient for the patient and/or parents/adoptive parents. The Investigator needs to conduct the following study procedures:

- Collection of patient's complaints
- Adverse events registration
- Assessment of concomitant therapy
- Study completion.

Upon the completion of all the procedures for Visit 4, the patient, as decided by the Investigator (in the absence of unresolved adverse events), completes the study.

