9.4 Methods for monitoring compliance with procedures

Compliance of the study product / placebo (adherence to therapy) will be assessed at Visits 2 and 3 according to the patient's electronic diary by checking the data entered by the patient's parent about taking the drug.

On Visit 1, one bottle of the prescribed drug will be given to the patient's parent / adoptive parent.

At Visit 3, the vial of the prescribed drug must be returned by the patient's parent / adoptive parent to the study center.

Monitoring compliance with the protocol procedures during the study is carried out by the investigator

According to the draft Patient information leaflet for Polyoxidonium, during therapy, patients from 1 to 2 years should receive the drug by 1 injection x 2 times per day sublingual (14 drugs in total / 14 doses), patients from 2 to 5 years - intranasal 1 injection in each nasal passage x 2 times a day (14 applications total / 28 doses), patients from 5 to 8 years old - intranasal 1 injection in each nasal passage 3 times a day (21 applications total / 42 doses), patients from 8 to 12 years old - intranasal for 2 injections per each nasal passage 2 times a day (14 applications in total / 56 doses). Possible omissions of taking the drug during the study:

No more than two misses with 2-fold SP / placebo.

No more than four passes - with 3-fold use of SP / placebo.

These conditions will allow maintaining the level of compliance not lower than 80% [21 - 24].

If compliance is less than 80%, patient data will not be included in the efficacy analysis.

Dosage of antipyretic drugs will be assessed during the study according to the Patient's Diary - by checking the completed data by the patient's parent about taking the drug on visits 2 and 3.

On Visit 1, one vial of the prescribed antipyretic drug will be given to the patient's parent / adoptive parent.

On Visit 3, the vial of the prescribed antipyretic drug must be returned by the patient's parent / adoptive parent to the study site.

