12.1 Justification of sample size

The study will include patients with a clinically confirmed diagnosis of ARVI (ICD-10 code: J00, J02, J04, J06), who will be randomized and distributed to one of two groups in a 1:1 ratio: Group 1 - patients who will be prescribed the study product as part of complex therapy; Group 2 - patients who will be prescribed a placebo as part of complex therapy.

A similar study of the efficacy, tolerability and safety of Polyoxidonium® in children with acute respiratory infections [5] involved 98 patients (52 in the group of the study product and symptomatic therapy, 46 in the placebo group and symptomatic therapy). The duration of fever and intoxication in the group of the study product was 2.6 ± 0.2 days, in the placebo group - 3.2 ± 0.2 days. Thus, the superiority of the efficacy of the drug Polyoxidonium® over the efficacy of a placebo in relation to the duration of the period of fever and intoxication was $-0,60 [-0,68; -0.52]$ days; the upper limit of the 95% confidence interval for the difference in efficacy of the study product and placebo was -0.52 days. Data from another study, in general, confirms the indicated efficacy values: in children who received Polyoxidonium® in the complex of therapy, compared with children who received only macrolide drugs, their body temperature decreased by 1-2 days earlier, shortness of breath, coughing, wheezing in the lungs (Kuzmenko L.G. The use of Polyoxidonium® in the treatment of frequently ill children, "EFFECTIVE PHARMACOTHERAPY. Pediatrics, No. 2, 2013).

In this study, the fever duration and intoxication period were selected as the main parameter characterizing the efficacy of the therapy. Value of $\delta = -0.52$ days is considered as the margin of excellence.

Calculation of the sample size is based on the following formula:

$$n = (Z_{\alpha} + Z_{\beta})^2 \cdot \frac{2 \cdot SD^2}{(\mu_o - \mu_p - \delta)^2}$$

where, Z_{α} and Z_{β} are critical values of the normal distribution corresponding to the established error levels α and β (α - and β -errors are 0.05 and 0.2, respectively), SD - a standard deviation [25 - 28].

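### Missed doses, a missed Day 12 call or an unlisted drug after the fever has ended can delete a recorded primary outcome from the only efficacy analysis

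*Combined protocol and SAP*

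**What the plan says.** **Outcome.** Sections 7.1 and 10 end the fever at two consecutive morning/evening readings of 36.9 °C or below. Section 9.2 takes these from a twice-daily home diary. For planning, Section 12.1 cites an earlier trial in which fever and intoxication lasted, "in the group of the study product was 2.6 ± 0.2 days, in the placebo group - 3.2 ± 0.2 days".

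**Analysis set.** Section 12.2 analyses efficacy in the per-protocol population only. The label ITT is used there for the safety set. Section 12.8 admits to the per-protocol set only children treated in strict accordance with the protocol, and Section 12.6 leaves missing data unfilled.

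**Removal rules.**
- Section 9.4: "If compliance is less than 80%, patient data will not be included in the efficacy analysis". The tolerated misses are two (twice daily) or four (three times daily).
- Section 13.3 lists as significant deviations: exceeding those skip limits over the whole treatment period, any product the protocol does not provide for, and "Significant deviations from visit schedules, including skipping any visit".
- Section 13.3 gives the consequence: "A patient with a significant deviation from the protocol should be excluded from the final analysis".
- Section 9.3.1 ends participation on forbidden therapy, with no date limit.

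**The Day 12 call.** It is Visit 4, and under Section 9.1.5 it "shall be held by telephone contact at a time convenient for the patient and/or parents/adoptive parents". Its procedures are complaints, adverse events and concomitant therapy. Appendix 5 schedules no temperature, Symptom Assessment Scale or IMOS at that contact. Section 9.1 says the call also monitors efficacy, but no efficacy instrument is attached to it, and Section 7.2 describes it as a safety assessment.

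**The concern.** The primary outcome is usually complete around day 3, while the removal rules run to Day 7 for doses and Day 12 for visits. A child who is afebrile on Day 2, and whose parent stops the spray on Day 5 or does not answer the Day 12 call, leaves the efficacy analysis with a complete fever duration on file.

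This kind of removal depends on what happens after the outcome, and the opportunity for it depends on the outcome itself, because an earlier end of fever leaves more doses to miss. If the product shortens fever, the two arms have different opportunities. At stake are valid outcomes, a 10% dropout allowance that was not sized for this, and the balance that randomisation gave the comparison.

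**Working it through.** **1. The plan's own figure.** Inputs from Section 12.1: Z values 1.645 and 0.842, SD 0.2, means 2.6 and 3.2, margin −0.52.

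n = (1.645 + 0.842)² × 2 × 0.2² / (2.6 − 3.2 + 0.52)² = 6.185 × 0.08 / 0.0064 = 77.3, so 78 per arm, as stated. With 10% added, 78 × 1.10 = 85.8, so 86 as in the synopsis. The allowance is therefore 86 − 78 = 8 children per arm.

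**2. Where the skip limits bite** (Sections 9.4 and 13.3).
- Twice daily, 14 applications: two misses leave 12/14 = 85.7%; a third leaves 11/14 = 78.6% and removes the child.
- Three times daily, 21 applications: four misses leave 17/21 = 81.0%; a fifth leaves 16/21 = 76.2% and removes the child.

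With twice-daily doses at 0, 0.5, …, 6.5 days, stopping just before the 6.0-day dose misses two and the child stays. Stopping at or before the 5.5-day dose misses at least three.

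**3. Doses still due after the fever.** On the same grid, 8 of 14 fall after day 2.6 and 7 of 14 after day 3.2. Stopping at the mean end of fever breaks the limit in both arms.

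**4. Exposure by fever length.** Assume each post-fever dose on twice-daily dosing is skipped independently with probability 0.2. The chance of more than two skips is:

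| Fever ends (day) | Doses left | Removed |
|---|---|---|
| 2 | 10 | 32% |
| 3 | 8 | 20% |
| 4 | 6 | 10% |
| 5 | 4 | 3% |

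**5. Illustration of loss and shift.** Assumptions: gamma durations with means 2.6 and 3.2, SD 0.8, 1.2 or 1.6 days; 20% of parents stop 1, 2 or 3 days after fever ends; twice-daily dosing; 2,000,000 children per arm. A stopper is removed if fever end plus lag is at most 5.5 days. Ranges are over the three SDs:

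| Lag | Active removed | Placebo removed | Difference (−0.60 with all children) |
|---|---|---|---|
| 1 day | 18–20% | 16–19% | about −0.62 |
| 2 days | 15–17% | 13% | −0.61 to −0.62 |
| 3 days | 10–11% | 4–8% | −0.57 to −0.58 |

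The sign changes for a simple reason. At a 1-day lag nearly all active stoppers are removed, so removal there is hardly selective. In placebo, fevers beyond 4.5 days escape, so its mean rises more. At a 3-day lag only fevers of 2.5 days or less are removable. These are mostly in the active arm, whose mean then rises more.

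**6. Power, on the plan's SD of 0.2 and true difference of −0.60.**

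| Per arm | One-sided 5% (sample-size formula) | Two-sided 95% interval (decision rule) |
|---|---|---|
| 86, none removed | 83.6% | 74.6% |
| 77, 10% removed | 79.9% | 69.9% |
| 68, 20% removed | 75.4% | 64.5% |

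**The case against.** **Individual review.** Section 13.3 has deviations considered case by case and classified by the sponsor before the statistical analysis, and Section 7.3.1 keeps statisticians blinded until database lock. This limits abuse. It does not change the rule: the same section ends by saying that children with significant deviations should be excluded, and it names these deviations as significant.

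**Full-course compliance is a legitimate per-protocol idea.** The stated purpose refers to benefit after 7 days of treatment, and the symptom and IMOS endpoints are read at Day 8. That stands for those endpoints. It does not justify deleting a fever duration recorded days earlier, and it gives no reason to remove a child for a missed Visit 4 call.

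**Later events may matter.** A reader might infer that nothing after the first pair of normal readings could affect the outcome. The documents do not settle this: there is no rule for recurrent fever, and Section 5.8 describes temperature rising again after a short improvement. The cut-off therefore needs a definition of the confirmed end of fever.

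**Size.** The stopping rate and the SDs of 0.8 to 1.6 are assumptions, and the plan's SD is 0.2. It is tempting to set a shift of about 0.03 day against the 0.08 day between −0.60 and −0.52 and conclude that it decides the trial. At the assumed SDs that does not follow. With 78 per arm the standard error is SD × √(2/78) = 0.128 to 0.256, and the chance of clearing the margin is Φ(0.08/SE − 1.96), about 9% to 5%, whatever is excluded.

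**Conclusion.** The concern holds on the text. Following the plan removes observed primary outcomes from the only efficacy analysis because of events after the fever has ended. For stopping after the fever, a shorter fever means greater exposure, so removal can differ by arm.

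The size is illustrative: about 10–20% of active and 4–19% of placebo children lost, and the difference moving to between about −0.57 and −0.62, under the assumptions in the working. On the plan's own inputs, a 20% loss costs 8 to 10 points of power.

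Two stronger readings are not supported. The bias has no fixed direction; it can favour or disfavour the product depending on when parents stop. Nor do the documents show that fast recoverers are the most exposed overall. They give no stopping data, only more than 2 or 4 skips remove a child, and slow recoverers have their own route out through antibacterial or other forbidden drugs.

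**What to change.** Amend Sections 9.4, 12.8 and 13.3, with Section 12.2 and the synopsis made consistent:

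1. For the primary endpoint, count only deviations dated up to the confirmed end of fever: applications due by then, forbidden or unlisted drugs started before then, and visits due before then.
2. Judge skipped applications against the existing absolute limits of 2 or 4, not a percentage of doses due. With four doses due, one miss gives 75% and would remove a fast recoverer. If doses are missed independently with probability 5% (assumed), active-arm removal would rise from about 3% under the present rule to 7–8% under a percentage-of-due rule.
3. State that a missed Visit 4 call never removes a child from efficacy.
4. Define the confirmed end of fever so that recurrence is handled identically in both arms.
5. For the Day 5 and Day 8 secondary endpoints, use the endpoint day as the cut-off.
6. Also report the primary endpoint in all randomised, treated children with an observed fever duration, regardless of later deviations.

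The cost is wording, one date-based flag and one extra analysis. The diary already records temperatures and dose times. The drawback is that the per-protocol set will differ by endpoint. These changes concern analysis sets only; treatment and withdrawal rules are untouched.

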14 QUALITY CONTROL AND ASSURANCE

Clinical centers licensed for medical practice, having accreditation and sufficient experience in conducting clinical studies will be selected for this study. Also, the clinical center should have medical personnel with the necessary qualifications and certified equipment necessary to conduct this study. The qualifications of the personnel of the study site participating in the study must be documented. The members of the research team must have the appropriate experience to complete the research tasks, as well as undergo the necessary training on the Protocol and research procedures.

The sponsor and organization conducting the research provides a quality control system that will guarantee the conduct of this study in accordance with the study protocol, ICH GCP rules and current requirements of the legislation of the Russian Federation.

All aspects of the study protocol should be complied with throughout the study. If changes are necessary, they should be discussed without delay by the Investigator, the Study Monitor and the Sponsor. Amendments to the study protocol should be made in writing and contain a detailed justification for the changes. Amendments must be submitted to the Ethics Council at the Ministry of Public Health of the Russian Federation and to the Local Ethical Committees of the centers.

Each deviation from the study protocol must be documented and justified by the Investigator (or the person designated by the Investigator) in the primary documentation, in the CRF and the study file.

14.1 Study monitoring and audit

Throughout the study, monitoring will be conducted to ensure that:

- rights and freedoms of patients are respected;
- the data entered in the CRF correspond to the primary documentation, are reliable, accurate and complete;
- the study is conducted in accordance with the approved latest version of the protocol and the existing amendments to it (when applicable), as well as other study documents.

- The study is conducted in accordance with the principles of ICH GCP and all applicable regulatory requirements of the Russian Federation.

The sponsor and study organizing company are responsible for assigning study monitors for quality monitoring. Monitoring of the study will be carried out regularly in accordance with the plan.

Investigators are required to provide the monitor with direct access to all necessary documents for monitoring, as well as to enable the monitor to:

- visit the study site, have access to the premises where the study is being conducted, the place where the study documentation is stored, the location of the study product;
- meet with members of the study team;
- check the correctness of filling out the CRF and reconcile the CRF with the primary medical documentation;
- reconcile drug registration; monitor compliance with the course of the study protocol.

The purpose of the audit, conducted separately and independently of routine monitoring and quality control functions, is to assess the compliance of the study with the Protocol, SOP, ICH GCP and regulatory requirements.

14.2 Sponsor's actions for non-compliance with applicable requirements.

Failure to comply with the Protocol, SOP and / or relevant regulatory requirements by the Investigator / study site, the IOC or the Sponsor's staff should lead to immediate action by the Sponsor to ensure their compliance. If serious and / or repeated incidents of non-compliance with the applicable requirements by the investigator / medical institution are found during the monitoring or audit, the CRO, the Sponsor must terminate the participation of the offending party in the study. If the participation of the Investigator / study site is terminated as a result of serious or repeated cases of non-compliance with applicable requirements, the Sponsor must notify the regulatory authorities hereof.

